### 12.5.3. Decision Rules

The study will either continue to the originally planned sample size if the result is “favorable”, stop for futility if the result is “unfavorable”, stop for success if the result is “overwhelming” or an increase will be made to the sample size if the result is “promising”. These decisions will be made based on the conditional power (CP), defined as the conditional probability that the result will exceed a critical value at the interim given the observed effect size  $\widehat{\delta}_1$  = difference between mean change in HDRS17 scores for the active versus sham groups at the interim look.

Notation:

n1= sample size at interim analysis.

n2= original sample size calculated based on assumed effect size.

nmax = the highest sample size the company is willing to use, nmax = 250 subjects and is based on a more conservative estimate of the effect size of 0.356.

CPmin= is the calculated minimum CP based on the ratios nmax/n2, n1/n2 and the target study power (80%).

The following are the decision rules for the interim analysis which will be performed upon accrual of ~80% of the sample size, 86 evaluable subjects:

- If the result is “Unfavorable”, i.e.  $CP < CP_{min} = 29.14\%$  (interim result is so disappointing that it is not worth increasing the sample size to retrieve conditional power), then stop the trial for futility.
- If the result is “Promising”, i.e.  $29.14\% \leq CP < 80\%$  the sample size is increased recover the targeted power of 80%. The sample size used will be either the new calculated sample size based on the conditional power (as described in Sample size re calculation using conditional power Jonathan S. Denne Statist. Med. 2001; 20:2645–2660) or the predetermined maximum sample size of 250 subjects.

 Neurolief Brain Innovation	MOOD: CLINICAL INVESTIGATION PLAN	Doc No.: CL-CIP-201 Rev: REV.3 / 09June2021 Pg. 73 of 92
--	--	--

- If the result is “Favorable”, i.e. CP  $\geq$  80% the interim results are sufficiently favorable, and the trial continues to the original sample size planned of 106 (before allowance for dropouts) without the need to adaptively increase the sample size.

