- If the result is “overwhelming” i.e. primary endpoint at the interim analysis is statistically significant at a 0.04108 level of significance, then stop the study for success. This was calculated based on an adaptive design with one interim analysis planned to either stop the study for futility or early success at the interim with a Lan-DeMets alpha spending approach using a Pocock type function, where at the interim the study will be stopped for success if the null hypothesis is rejected at an alpha level of 0.04108.

Note that the interim analysis will be conducted on all populations (ITT, mITT, PP and mYITT analysis sets, see **Section 12.7**), and the study will be stopped due to futility only if the interim effects in all populations fall below the threshold.

The un-blinded statistician will also calculate the sample size required to test the null hypothesis to achieve 80% power at 4.108% level of significance given the current trend.

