#### **12.5.4. Controlling the Alpha Level for the Primary Endpoint**

The overall alpha level for this study is 5%. According to [Müller 2001; Jonathan 2001 Broberg 2013 and Siu 2001], planning an interim analysis that permits an increase in the sample size as described above does not inflate the type I error.

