### **12.8.2. Significance Level and Handling of Type I Error**

#### **Type I Error:**

The overall significance level for this study is 5% using two-tailed tests, except for treatment by site interaction that will be tested at a significance level of 10% and the test for early efficacy at the interim look.

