The principal statistical analysis will be a comparison between the treatment groups, derived from the visit by treatment group interaction term from the model. The adjusted mean change from baseline in HDRS-17 scores at 8 weeks post treatment initiation will be estimated from the model (LS Means) interaction term for each group, as well as the difference between the adjusted means, and will be presented together with 95% confidence intervals. The null hypothesis will be rejected in favor of the alternative hypothesis and the study deemed

successful if the p-value is <0.05 and the mean change HDRS-17 in the active group is higher than that of the sham group.

The primary analysis model uses likelihood-based inference that is valid under a missing at random assumption.

Cohen's D will be calculated and presented as well as a measure of the clinical effect size of the change from baseline HDRS-17 at week 8. An effect size can also be calculated using methods described in "Effect sizes for growth-modeling analysis for controlled clinical trial in the same metric as for classical analysis", *Psychol Methods*. 2009 March; 14(1): 43-53), where $ES = \text{difference between LSmeans} / \text{Pooled SD of baseline HDRS-17 score}$.

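### The 0.04108 interim efficacy level does not match its stated spending rule at 86 of 106 subjects, and the final test stays at p<0.05 with no adjustment for that look

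*Protocol*

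**What the plan says.** Protocol 12.5.3 places the interim analysis "upon accrual of ~80% of the sample size, 86 evaluable subjects". The original evaluable size is 106. At that look, "the study will be stopped for success if the null hypothesis is rejected at an alpha level of 0.04108", a level said to be derived "with a Lan-DeMets alpha spending approach using a Pocock type function". The same section has the unblinded statistician compute a sample size for "80% power at 4.108% level of significance given the current trend". It also sets the futility bound CPmin at 29.14% and the maximum size at 250. It defines conditional power by reference to a critical value but gives no number for it.

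On the overall error rate, Protocol 12.8.2 says "The overall significance level for this study is 5% using two-tailed tests", with exceptions only for the treatment-by-site interaction and the interim efficacy test. SAP 9.1 repeats this. Protocol 12.5 says the final analysis uses the conventional test. Protocol 12.9.1 and SAP 11.5.1 then declare the study "successful if the p-value is <0.05", provided that the difference favours the active arm. SAP 2.2.1 reports that the interim took place at 86 evaluable subjects, was classed as Favorable, and led to continuation at the original planned size.

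**The concern.** Two things do not fit together. First, a decision threshold should be recoverable from the rule said to produce it, and this one is not, given the numbers in the plan. Second, and more important, a design that allots most of its alpha to an interim efficacy test must lower the final level. No section gives a lowered level: the interim test is exempted from 5%, but the final test keeps all of it.

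At stake is the claim that the primary comparison in a pivotal trial is controlled at 5%. A final p-value between the adjusted level and 0.05 would be called a success under SAP 11.5.1 although a 5% design would not allow it. The reuse of 4.108% for a sample-size calculation adds to the uncertainty about which critical value governs which step.

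**Working it through.** **Inputs.** Overall two-sided alpha 0.05 (Protocol 12.5.4, 12.8.2); interim n1 = 86, planned n2 = 106, nmax = 250, target power 80%, CPmin 29.14%, interim level 0.04108 (12.5.3); final level 0.05 (12.9.1; SAP 11.5.1). Information is taken as proportional to subjects, with normal approximations.

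**1. The interim level.** Pocock-type spending is α(t) = 0.05 × ln(1 + (e − 1)t). At a first look the nominal level equals the alpha spent.
- t = 86/106 = 0.8113: 0.05 × ln(2.394) = 0.0436.
- t = 0.80: 0.05 × ln(2.375) = 0.0432.
- Solving α(t) = 0.04108 gives t = 0.7415, and 86/0.7415 ≈ 116 subjects.

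Other forms at 86/106 also miss: O'Brien-Fleming-type 0.0296 or 0.0257 (two forms), linear 0.0406, Hwang-Shih-DeCani with γ = 1 0.0440, equal Pocock boundaries 0.0351. So 0.04108 is not reproduced from the stated inputs.

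**2. Overall error with 0.04108 then 0.05.** Under the null, Z1 and Z2 are bivariate normal with correlation √t. The bounds are z = 2.043 (0.04108) and 1.960 (0.05).
- Fixed N, non-binding futility, t = 86/106: 0.0411 + P(|Z1| < 2.043, |Z2| ≥ 1.960) = 0.0411 + 0.0235 = 0.0646.
- Same, t = 0.80: 0.0411 + 0.0240 = 0.0651.
- Binding futility at CPmin (Z1 = 1.550), active-better direction: P(Z1 ≥ 2.043) = 0.0205, plus P(1.550 < Z1 < 2.043, Z2 ≥ 1.960) = 0.0082. The total is 0.0287 one-sided, or 5.7% two-sided equivalent.
- Same, also crediting the increase to 80% conditional power capped at 250: about 0.0271 one-sided, or 5.4%.

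**3. The final level that holds 5%.** With 0.04108 spent, 0.05 − 0.04108 = 0.00892 remains. Solving P(|Z1| < 2.043, |Z2| ≥ c) = 0.00892:
- t = 86/106: c = 2.199, two-sided level 0.0279.
- t = 0.80: c = 2.209, two-sided level 0.0272.

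**4. Which critical value lies behind CPmin.** In the promising-zone formula with critical value c, the lower limit z solves √((250 − 86)/(106 − 86)) × (c√106 − z√86) + z√86 = c√250. Conditional power there is 1 − Φ[(c√106 − z√86)/√20 − z√20/√86].
- c = 1.960: z = 1.550, CPmin = 29.13%, against the stated 29.14%.
- c = 2.043 (4.108%): z = 1.616, CPmin = 28.34%.

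The stated CPmin therefore appears to rest on 5%. This is an inference, since the protocol gives no number.

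**The case against.** The best defence of 0.04108 is that the protocol does not say 106 was the denominator. A Pocock-type group-sequential design needs a larger maximum size than a fixed one. The inflation factor for 80% power with the look at 86/116 is about 1.113, and 104 × 1.113 ≈ 116, where 104 is the normal-approximation total at an effect size of 0.55. At 86/116 the function gives 0.0411. So the number may come from the stated rule with an unreported denominator. That is conjecture, because 116 appears nowhere in the plan, but it does mean that a reader who infers a plain miscalculation goes further than the documents allow. What stands is that the information fraction is missing and does not match the stated 86 of 106.

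A reader might also infer that the mismatch inflates the interim error. It does not: 0.04108 is stricter than 0.0436.

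Nor is 6.5% the plan's error rate without qualification. It ignores the futility stop and the sample-size increase, and crediting them as binding brings it to 5.4% to 5.7%. Full credit is hard to justify, because 12.5.3 stops for futility only if all four analysis sets fall below the threshold. Even with full credit the figure exceeds 5%. The argument in Protocol 12.5.4 does not close the gap: it concerns increasing the sample size, not an efficacy look followed by a full-level final test.

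Finally, the 4.108% sample-size calculation can be read as an addition to the conditional-power re-estimation. SAP 2.2.1 reports no increase, so the documents do not support an inference that it altered this trial's size.

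**Conclusion.** The point holds in two parts of unequal weight. The lesser part is documentary: 0.04108 does not follow from the stated function at the stated look, and its information fraction should be disclosed. The greater part is the unadjusted final test. As written, two-sided type I error is about 6.5% with fixed N and non-binding futility, and roughly 5.4% to 5.7% under the more generous assumptions, against a stated 5%. These figures assume information proportional to subjects, one analysis set, and 106 evaluable subjects at the end.

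The steps also appear to use different critical values: 4.108% for one sample-size calculation and, by inference, 5% for CPmin. With 1.96, conditional power of 80% at 86/106 needs Z1 ≥ 2.095 (p ≤ 0.036), which already lies inside the 0.04108 stopping region. A reader might infer that the reported Favorable outcome was misclassified. The documents do not support that, since they give neither the interim p-value nor the critical value or deciding analysis set. They show only that the rules need one stated critical value.

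**What to change.** Keep 0.04108 as the interim alpha spent and state the information fraction and total alpha behind it. Do not move the boundary to 0.0436: the look has been done.

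In SAP 11.5.1, replace p<0.05 with the final two-sided level that holds overall alpha at 5% given 0.04108 spent and the realised information fraction. That is about 0.0279 at 86/106 and 0.0272 at 0.80; the exact value depends on the final evaluable number, which the documents do not give. Carry the same level into the gate for the secondary endpoints in SAP 9.2, which also reads 0.05. Use that one critical value wherever conditional power or a sample-size recalculation is defined, and record which value was used at the interim.

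The cost is wording plus a stricter threshold. For a single test with 53 per group at effect size 0.55, the normal approximation gives 0.55 × √26.5 = 2.83. Power is then Φ(2.83 − 1.96) ≈ 81% at 5% and Φ(2.83 − 2.20) ≈ 74% at 0.0279. The two-look design as a whole loses less, because interim success also counts. SAP Section 1 lets the SAP prevail over the protocol, and Section 6 says the treatment code was unrevealed when the SAP was finalised, so the level could be set there without knowledge of the result.

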#### **12.5.4. Controlling the Alpha Level for the Primary Endpoint**

The overall alpha level for this study is 5%. According to [Müller 2001; Jonathan 2001 Broberg 2013 and Siu 2001], planning an interim analysis that permits an increase in the sample size as described above does not inflate the type I error.

### **12.6. Randomization**

Eligible subjects will be randomly allocated (with a 1:1 ratio) to one of the following 2 treatment groups based on a randomization scheme using the permuted block method stratified by center:

- Active (Relivion®DP) stimulation
- Sham stimulation

The randomization scheme will be prepared by the study statistician using the SAS (version 9.4.) random number procedure. The block size will be random, and all study personnel will be therefore blinded to the randomization block size.

### **12.7. Study Analysis Populations**

#### **12.7.1. Intent-to-Treat (ITT) Population:**

The intent-to-treat (ITT) population will include all subjects aged 22 through 70 enrolled in the study as randomized. This population will include all subjects who receive at least one active/sham treatment.

 Neurolief Brain Innovation	MOOD: CLINICAL INVESTIGATION PLAN	Doc No.: CL-CIP-201 Rev: REV.3 / 09June2021 Pg. 74 of 92
--	--	--

According to the ITT principle all subjects will be analyzed in the treatment group as assigned by randomization.

#### **12.7.2. Modified Intent-to-Treat (mITT) Population:**

The modified intent-to-treat (mITT) population will include all subjects from the ITT set enrolled in the study, who completed the minimal stimulation time required by the protocol and have no post randomization exclusion criteria. The mITT analysis set will be analyzed in the treatment group as treated.

#### **12.7.3. Per-Protocol Population:**

All subjects from mITT set that complete the 8-week treatment period (without withdrawal) and without any major protocol deviations.

#### **12.7.4. Modified Younger Intent-to-Treat (mYITT) Population:**

The modified younger intent-to-treat (mYITT) population will include all subjects from the ITT set enrolled in the study including subjects aged 18-21, who completed the minimal stimulation time required by the protocol and have no post randomization exclusion criteria. The mYITT analysis set will be analyzed in the treatment group as treated.

#### **12.7.5. Statistical Analysis of Analysis Sets**

Safety assessments will be performed on the ITT and mYITT analysis set.

The mITT cohort will serve as the principal data analysis set for the primary and secondary statistical evaluation of the efficacy endpoints. The primary, secondary and exploratory efficacy assessment will also be performed on the per protocol (PP) analysis set as a sensitivity analysis and to show consistency of study results. The primary and secondary efficacy analyses will also be performed on the mYITT analysis set.

### **12.8. Statistical Analysis**

#### **12.8.1. General Considerations**

Statistical analyses will be performed using SAS® v9.4 (SAS Institute, Cary NC, USA). Statistical analyses and reporting will be performed in compliance with FDA Guidance E6 GCP, 21 CFR part 812, E9 and ISO 14155.

Study data will be summarized with descriptive statistics and presented in tables and figures. Continuous variables will be summarized by a mean, standard deviation, minimum, median and maximum and

 Neurolief Brain Innovation	MOOD: CLINICAL INVESTIGATION PLAN	Doc No.: CL-CIP-201 Rev: REV.3 / 09June2021 Pg. 75 of 92
--	--	--

categorical variables by a count and percentage. For comparison of means (continuous variables), the two-sample t-test or the Wilcoxon rank sum test will be used as appropriate. For comparison of proportions (categorical variables), the chi-squared test or Fisher's exact test will be used as appropriate. If multiple measurements are taken in a single subject, statistics described below will be appropriately modified to accommodate the within subject correlation.

Deviations from the planned analysis will be described, with proper justification, in the clinical study report.

### **12.8.2. Significance Level and Handling of Type I Error**

#### **Type I Error:**

The overall significance level for this study is 5% using two-tailed tests, except for treatment by site interaction that will be tested at a significance level of 10% and the test for early efficacy at the interim look.

#### **Controlling the Overall Type I Error:**

The hierarchy approach will be adopted for the primary and secondary endpoints to control type I error due to multiple endpoint testing. Thus, the primary endpoint will first be tested and only if  $p \leq .05$ , will the secondary endpoints be tested. For the three secondary performance endpoints, the Benjamini–Hochberg step-up method will be used to adjust the p-values.

### **12.8.3. Demographic and Other Baseline Characteristics**

Demographic and baseline condition related characteristics will be tabulated and compared between the study groups by data type. Continuous variables will be summarized by a mean, standard deviation, minimum, median and maximum and categorical variables by a count and percentage. The statistical evaluation of baseline characteristics will include all available data from the ITT population.

These data will include:

- Demographic data
- Medical history
- Psychiatric history
- Previous and Current Psychotropic Medication
- Type, dose and frequency of concomitant medications

 Neurolief Brain Innovation	MOOD: CLINICAL INVESTIGATION PLAN	Doc No.: CL-CIP-201 Rev: REV.3 / 09June2021 Pg. 76 of 92
--	--	--

#### 12.8.4. Disposition of Subjects

The number of subjects who entered the study and completed each stage of the study will be provided and compared between the study groups, as well as the reasons for all post randomization discontinuations, grouped by major reason, e.g., lost to follow-up, adverse event, poor compliance, did not administer any treatment (with reasons). A list of discontinued patients, protocol deviations and subjects excluded from the efficacy analysis will be provided as well.

Time to withdrawal will also be assessed and presented by Kaplan-Meier curves and will be compared using the Log-Rank test if relevant.

### 12.9. Efficacy Analysis

#### 12.9.1. Primary Efficacy Analyses

The primary efficacy endpoint is the change from baseline to 8 weeks post treatment initiation in HDRS17 score.

The change in HDRS17 from baseline to 8 weeks post treatment initiation will be compared between the treatment groups using a repeated measures analysis of covariance (ANCOVA, SAS® MIXED procedure). The model will include the following fixed effects: treatment group, visit, treatment group by visit interaction with Baseline HDRS17, and center entered as covariates. Baseline HDRS17 scores will be entered as a continuous variable so that the potential for co-linearity problems will be minimized. The treatment group by center interaction will be evaluated as well, but not as part of the principal statistical evaluation. Additionally, the center variable will be grouped by country as US versus out of US (OUS) and the analyses as for center will be repeated on this new variable.

The unstructured covariance matrix structure will be used. If the model does not converge, then either the compound symmetry or autoregressive (whichever model has the lower AIC statistic) covariance matrix structure will be used instead. At this time point (up to 8 weeks) we do not expect a high proportion of dropouts, as a placebo effect of the sham treatment is expected and was taken into consideration in the design of the study. Thus, any missing data at 8 weeks post treatment initiation can be considered missing at random. Therefore, since repeated measures ANOVA is also an imputation method, for this evaluation no other method of imputation of missing data is considered beyond the model estimates. Nevertheless, should the missing at random assumption prove to be incorrect, a sensitivity analysis using methods for data imputation mentioned in section 12.9.5 will be performed.

The principal statistical analysis will be a comparison between the treatment groups, derived from the visit by treatment group interaction term from the model. The adjusted mean change from baseline in HDRS17 scores at 8 weeks post treatment initiation will be estimated from the model (LS Means) interaction term for each group as well as the difference between the adjusted means and presented together with 95% confidence intervals.

 Neurolief Brain Innovation	MOOD: CLINICAL INVESTIGATION PLAN	Doc No.: CL-CIP-201 Rev: REV.3 / 09June2021 Pg. 77 of 92
--	--	--

The null hypothesis will be rejected in favor of the alternative hypothesis and the study deemed successful if the p-value is <0.05 and the mean change HDRS17 in the active group is higher than that of the sham group.

Cohen's D will be calculated and presented as well as a measure of the clinical effect size of the change from baseline HDRS17 at week 8. An effect size can also be calculated using methods described in "Effect sizes for growth-modeling analysis for controlled clinical trial in the same metric as for classical analysis", *Psychol Methods*. 2009 March; 14(1): 43-53), where ES = difference between LSmeans / Pooled SD of baseline HDRS17 score.

**Subset Analyses of Primary Endpoint:**

Significant or important variables, such as demographic or other baseline patient characteristics or concomitant medications (depending on use), will be entered as additional covariates in the primary efficacy endpoint ANCOVA model to evaluate their effect on the change from baseline HDRS17 score.

- Use of concomitant medications.
- Blinding assessment
- US vs. OUS sites

The effect of potential unblinding will be evaluated as a sensitivity analysis, where an additional binary variable identifying subjects unblinded versus those not un-blinded will be added to the ANCOVA model as a covariate.

### **12.9.2. Secondary Efficacy Analyses**

- Proportion of responder subjects- defined as the percent of subjects achieving at least 50% reduction from baseline in their HDRS17 total score, 8 weeks post Relivion®DP treatment initiation- will be summarized by a count and percentage and compared between the groups with a chi-squared test and a Fisher's exact test. As an additional measure of effect size the NNT will be presented.
- Proportion of subjects achieving remission- defined as the percent of subjects with HDRS17 score≤7 at 8 weeks post Relivion®DP treatment initiation- will be summarized by a count and percentage and compared between the groups with a chi-squared test and a Fisher's exact test. As an additional measure of effect size the NNT will be presented.
- Mean Change in depressive symptoms, measured by MADRS total score, from baseline to week-8 post treatment initiation - will be compared between the groups using a similar model as the primary endpoint.

 Neurolief Brain Innovation	MOOD: CLINICAL INVESTIGATION PLAN	Doc No.: CL-CIP-201 Rev: REV.3 / 09June2021 Pg. 78 of 92
--	--	--

